#### **4.5.1 Inferential methods**

The study is exploratory and no formal null hypothesis is set. No adjustments for multiple comparisons will be applied.

### **4.6 Exploratory analyses and deviations**

Exploratory data-driven analyses can be performed with the caveat that any statistical inference will not have any confirmatory value.

Deviations from the original statistical plan will be documented in the clinical study report.

## APPENDIX 1 SCHEDULE OF ASSESSMENTS

Visit	Screening	V1*	V2	V3	V4	V5	V6	V7	V8	EOT or ET	Unscheduled Visit 	Follow-Up
Week	Up to 6 weeks	1	2	5	6	9	13	14	17	21	N/A	29, 37, 45
Day*	-42 ~ 0	1 	8 (□1)	29  (□3)	36 (□3)	57 (□3)	85  (□3)	92 (□3)	113 (□3)	141 (□7)	N/A	197, 253, 309 (□7)
Informed Consent	X											
Inclusion/exclusion criteria	X	X										
Medical history & demographics	X											
Medication review	X	X	X	X	X	X	X	X	X	X	X	X
AE/SAE review 		X	X	X	X	X	X	X	X	X	X	X
Vital signs 	X 	X 	X	X	X	X	X	X	X	X	X	X
Physical Exam 	X	X		X		X		X		X	X	X 
Neurological Exam 	X	X		X		X		X		X	X	X 
ECG 	X	X		X		X		X		X	X	
MRI		X 									X	
Randomization		X										
HIV, HCV, HBV test	X			X	X	X	X	X	X	X	X	X
SARS-CoV-2 antigen test (when required) 	X			X	X	X	X	X	X	X	X	X

CHDR1853

Visit	Screening	V1*	V2	V3	V4	V5	V6	V7	V8	EOT or ET	Unscheduled Visit 	Follow-Up
Week	Up to 6 weeks	1	2	5	6	9	13	14	17	21	N/A	29,37,45
Day*	-42 ~ 0	1 	8 (□1)	29  (□3)	36 (□3)	57 (□3)	85  (□3)	92 (□3)	113 (□3)	141 (□7)	N/A	197, 253, 309 (□7)
Pregnancy test 	X	X		X			X				X	
Clinical chemistry 	X	X		X			X		X	X	X	
Haematology 	X	X		X			X		X	X	X	
Coagulation 	X											
Urinalysis 	X	X		X			X		X	X	X	
Urine drug screen 	X	X									X	
Alcohol breath test 	X	X									X	
Inflammatory markers 	X	X		X			X		X	X	X	
Cytokines		X 		X 			X 		X	X	X	
Antibodies in blood 	X	X		X			X		X	X	X	
Free and total aSyn 		X		X			X		X	X	X	
ELISPOT 		X							X	X 		
HLA typing 		X										
Blood collection for future research 		X	X	X	X	X	X	X	X	X	X	

CHDR1853

Visit	Screening	V1*	V2	V3	V4	V5	V6	V7	V8	EOT or ET	Unscheduled Visit 	Follow-Up
Week	Up to 6 weeks	1	2	5	6	9	13	14	17	21	N/A	29, 37, 45
Day*	-42 ~ 0	1	8 (□1)	29 (□3)	36 (□3)	57 (□3)	85 (□3)	92 (□3)	113 (□3)	141 (□7)	N/A	197, 253, 309 (□7)
CSF collection 		X								X	X	X 
Study Drug IM Injection		X		X			X					
Injection Site Reaction review 		X 	X	X 	X	X 	X	X		X		
For Part B only												
Hoehn and Yahr		X										
MDS-UPDRS (Parts II to III  )			X							X	X	X 
DaTscan			X 									
MoCA		X								X		X 

AE=adverse event; CSF=cerebrospinal fluid; ECG=electrocardiogram; EOT = End of Treatment; ET = Early Termination; HBV = Hepatitis B virus; HCV=hepatitis C virus; HIV = human immunodeficiency virus; IM=intra-muscular; MDS-UPDRS=Movement Disorders Society – Unified Parkinson’s Disease Rating Scale; MoCA = Montreal Cognitive Assessment; MRI=magnetic resonance imaging; SAE=serious adverse event

\* Time points for all visits are relative to Day 1 (day of first IMP administration). Every effort should be made to schedule visits as close as possible to the time point specified in the Schedule of Assessments. If a visit cannot be scheduled within the specified window, the timing of the visit and procedures should be discussed with the Sponsor.

1. Prior to administration of study IP at each applicable visit. Screening and V1 visits can be rescheduled if measured for moderate or severe illness and/or fever >38.0° Celsius within 1 week prior to visit.
2. AEs/SAEs recorded from time of informed consent up to and including Follow-up.
3. Also performed 45 minutes (+/- 15 minutes) and approximately 6 hours after administration of study IP at each applicable visit.
4. Including height (screening only); no need to repeat weight measurement for post-injection vital signs.
5. Full neurological exam at screening and last FU visit; brief neurological examination at other visits.

6. ECG in triplicate.
7. MRI will be performed between Screening and baseline (V1). For participants who were screen failed and subsequently re-screened to accommodate deployment of the COVID-19 booster vaccination, the original MRI performed during the initial screening can be accepted provided it was performed within 90 days of the start of treatment (Day 1).
8. For females of childbearing potential only, blood pregnancy test at screening and urine test at other visits. For part B, a urine pregnancy test will also be performed prior to DaTscan (in addition to the blood pregnancy test).
9. **Specific measurements are listed in Section Error! Reference source not found. of the protocol. Hematology and chemistry results will be available prior to the first study drug administration.**
10. Inflammatory measures in blood will include: C-reactive protein (CRP), erythrocyte sedimentation rate (ESR). At Screening only: antinuclear antibody (ANA), IgM rheumatoid factor (RF) and anti-cyclic citrullinated peptide (anti-CCP). CRP level results will be available prior to study drug administration at each applicable visit. For participants who have undergone COVID-19 booster vaccination, inflammatory markers at Screening may be repeated if results at Screening are not within acceptable limits as required by the protocol.
11. Additional blood samples will be collected for future medical research in participants who consent.
12. Hoehn & Yahr for Screening only.
13. Historic DaTscan is acceptable.
14. Participants will stay for 6 hours after injection for safety observation. Participants will have a 24-hour telephone call. Daily injection site review and temperature recording will be done at home by the participant for 6 days, starting from the day after study drug administration.
15. Individual tests will be performed at Investigator's discretion.
16. Antibody measures in blood, including but not limited to: anti-aSyn target epitope (monomers, oligomers and fibrils may be analysed), anti-UB1Th, anti-CpG1.
17. Full physical examination at screening and last FU visit, brief physical examination during the other visits.
18. Performed at the last follow-up visit only.
19. Only performed if PBMC sample for ELISpot not collected at V8.
20. The pre-dose cytokine blood samples analysis for (Part A) will include: IFN- $\gamma$ , IL-1 $\beta$ , IL-2, IL-4, IL-6, IL-8, IL-10, IL-12p70, IL-13 and TNF- $\alpha$ . The cytokine panel in Part B is based on the observed effects in Part A, and will include: IFN- $\gamma$ , IL-2, IL-6, IL-8, TNF- $\alpha$  and CXCL 10. Part B cytokine blood samples will be collected pre-dose and approximately 6 hours post-dose at each applicable visit, only analysed at PI's discretion if clinically indicated, otherwise, will be analysed at the end of study.
21. Biomarker-based efficacy will be measured by detecting aSyn aggregates in pre- and post-immunization CSF samples of PD patients using the protein misfolding cyclic amplification (PMCA) assay.
22. SARS-CoV-2 antigen test will be performed only in case of symptoms possibly related to COVID-19 and/or in accordance with prevailing local guidelines as described in the COVID-19 risk assessment and mitigation strategies for Study UB-312-101 on file at the investigational site.

## APPENDIX 2 PROCEDURE & SYNTAX

Analysis	Procedure and Code
AN(C)OVA	
For the SAS script:
 
 
▪ period = occasion
 
▪ time = expdelta
 
▪ subject = subjectnr
 
▪ baseline=pre&var
 
 
SAS Proc MIXED Procedure:
 
Repeatedly measured:
 <pre>proc mixed data=mix order=internal nobound ; class subjectnr treatment expdelta occasion ; model &var=treatment occasion expdelta treatment*expdelta pre&var/ ddfm=KR; random subjectnr subjectnr*treatment subjectnr*expdelta/type=vc ; run;</pre> 
Single measured:
 <pre>proc mixed data=mix order=internal nobound ; class subjectnr treatment occasion ; model &var=treatment occasion pre&var/ ddfm=KR; random subjectnr/type=vc ; run;</pre>

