#### 4.5 Analysis of efficacy endpoints

All observed and change from baseline efficacy endpoints will be listed by treatment group, subject and visit. Individual graphs by visit will also be generated.

All observed and change from baseline efficacy endpoints with multiple post-baseline measurements (including but not limited to levels of anti-aSyn, anti-UBITH and anti-CpG1 antibody titers in serum and their antibody parameters of  $C_{max}$ ,  $t_{max}$ ,  $AUC_{last}$  and  $t_{1/2}$ , which are derived by non-compartmental analysis and total and free aSyn concentrations in blood) will be summarized using descriptive statistics of n, mean, SD, SEM, median, Min and Max by treatment group, visit (and time when applicable), and will also be presented graphically as mean over time, with standard deviation as error bars.

All observed and change from baseline efficacy endpoints with single post-baseline measurement (including but not limited to levels of anti-aSyn, anti-UBITH and anti-CpG1 antibody titers in CSF and their antibody parameters of  $C_{max}$ ,  $t_{max}$ ,  $AUC_{last}$  and  $t_{1/2}$ , which are derived by non-compartmental analysis and total and free aSyn concentrations in CSF, T-cell ELISpot specific for the immunizing peptide as well as MDS-UPDRS Parts II and III sub scores and total scores) will be summarized using descriptive statistics of n, mean, SD, SEM, median, Min and Max by treatment group, and will also be presented graphically as mean in a bar graph, with standard deviation as error bars.

To establish whether significant treatment effects can be detected on the observed efficacy endpoints with multiple post-baseline measurements, such as serum levels of anti-aSyn, anti-UBITH and anti-CpG1 antibody titers in blood, each parameter will be analysed with a mixed model analysis of covariance (ANCOVA) with treatment, time and treatment by time as fixed factors and subject as random factor and the (average) baseline measurement as covariate.

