The efficacy endpoints of levels of anti-aSyn, anti-UBITH and anti-CpG1 antibody titers in serum and in CSF will initially be analysed without transformation, but if the data suggest otherwise, log-transformation may be applied. Log-transformed parameters will be back-transformed after analysis where the results may be interpreted as percentage change. Residual Q-Q plots are produced to check the assumption of normality of the error term in the mixed effects models as described above. This is done by visual inspection and the Shapiro-Wilk test statistic.

The observed efficacy endpoints with single post-baseline measurement, such as levels of anti-aSyn, anti-UBITH and anti-CpG1 antibody titers in CSF, will be analysed with a mixed model analysis of variance (ANOVA) with treatment as fixed factors and subject as random factor and the (average) baseline measurement as covariate.

The Kenward-Roger approximation will be used to estimate denominator degrees of freedom and model parameters will be estimated using the restricted maximum likelihood method.

The general treatment effect and specific contrasts will be reported with the estimated difference and the 95% confidence interval, the least square mean estimates and the p-value. Graphs of the Least Squares Means (LSM) estimates over time by treatment group will be presented with 95% confidence intervals as error bars, as well as change from baseline LSM estimates.

The following contrasts will be calculated within the model using observed data:

- Treatment with 3 vaccinations of 40 $\mu$ g UB-312 versus pooled Placebo
- Treatment with 3 vaccinations of 100  $\mu$ g UB-312 versus pooled Placebo
- Treatment with 1 vaccination of 40  $\mu$ g, followed by 2 vaccinations of 300  $\mu$ g UB-312 versus pooled Placebo
- Treatment with 3 vaccinations of 300  $\mu$ g UB-312 versus pooled Placebo
- Treatment with 1 vaccination of 40  $\mu$ g, followed by 2 vaccinations of 1000  $\mu$ g UB-312 versus pooled Placebo
- Treatment with 3 vaccinations of 1000  $\mu$ g UB-312 versus pooled Placebo
- Treatment with 3 vaccinations of 2000  $\mu$ g UB-312 versus pooled Placebo

Notes:

- (1) Change from baseline values calculated at subject level for each efficacy endpoint will only be used for descriptive purposes.
- (2) Above contrast will be adjusted to obtain for change from baseline endpoints.
- (3) The treatment groups across the cohorts will also be compared pairwise.

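### SAP Appendix 2 does not fit the design or Section 4.5: CSF titres and MDS-UPDRS go to a model with no time term, and the repeated-measures code carries redundant random terms

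*SAP*

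**What the plan says.** **Endpoints with several post-baseline values.** SAP Section 4.5 specifies a mixed-model ANCOVA with "treatment, time and treatment by time as fixed factors and subject as random factor" and baseline as covariate. The Appendix 2 code for repeated measurements has the random line "random subjectnr subjectnr*treatment subjectnr*expdelta/type=vc". It also adds a fixed effect called occasion, explained only by "period = occasion", and the procedure line reads "proc mixed data=mix order=internal nobound".

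**Endpoints with a single post-baseline value.** Section 4.5 puts CSF antibody titres, CSF total and free aSyn, T-cell ELISpot and MDS-UPDRS Parts II and III in this class. It states that such endpoints "will be analysed with a mixed model analysis of variance (ANOVA) with treatment as fixed factors and subject as random factor", with baseline as covariate. The matching Appendix 2 code has treatment, occasion and baseline as fixed effects and "random subjectnr/type=vc". It has no time variable.

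**Schedule.** Protocol Table 1 and SAP Appendix 1 both place CSF collection and MDS-UPDRS at the end-of-treatment visit (Week 21) and, through footnote 18, at the last follow-up visit (Week 45). SAP Section 2.3 also lists MDS-UPDRS ratings at baseline, EOT/ET and the last follow-up.

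**Inference.** Section 4.5 calls for REML, Kenward-Roger degrees of freedom, 95% confidence intervals and p-values for each regimen against pooled placebo.

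**The concern.** There are two separate faults.

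1. **CSF titres and MDS-UPDRS are in the wrong class.** They have two scheduled post-baseline values, 24 weeks apart, but the assigned model cannot distinguish them. The SAP does not say whether one row or both rows enter. Anti-aSyn antibody in CSF is part of a primary objective, so the plan leaves open which quantity is estimated: the Week 21 effect, the Week 45 effect, or a mixture.

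2. **The repeated code looks written for a crossover.** A subject-by-treatment variance can be separated from the subject variance only if participants receive more than one treatment, and a period term presupposes periods. Here each participant stays in one regimen. The code therefore differs from Section 4.5 and contains variance components that the data cannot separate. Two programmers, one working from the text and one from the code, would fit different models to the serum titres.

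**Working it through.** **Inputs.** Part A: 8 + 6 × 7 = 50 participants, with pooled placebo 2 + 6 × 1 = 8 and seven arms of 6 (SAP 1.9, 1.10, 3.6). Part B: 2 × 10 = 20, with arms of 7 and 7 and pooled placebo of 6 (protocol synopsis). Post-baseline visits: Weeks 2, 5, 6, 9, 13, 14, 17, 21, 29, 37 and 45, so 11. One antibody sample at each of these visits is an assumption, because the antibody row is damaged in the extracted schedules. The SAP gives no degrees of freedom or standard error to reproduce.

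**Check 1: code for single measurements**
- *One row per participant.* The subject effect has one level per row, so its covariance matrix is the identity, the same as the residual. The REML information matrix has rank 1 for 2 components. Only the sum of the two variances is estimable, and the model reduces to ordinary ANCOVA. Degrees of freedom are 50 − 8 groups − 1 covariate = 41 in Part A and 20 − 3 − 1 = 16 in Part B.
- *Two rows per participant (Weeks 21 and 45).* The information matrix has rank 2 of 2, so the model is identified. It has one treatment parameter per arm. With complete data the estimated difference is (d21 + d45)/2, where d21 and d45 are the differences from placebo at the two visits. If Week 45 values are missing unevenly, the weights shift and any change over time common to all arms enters the comparison.
- If occasion were used as a visit label it would add a visit main effect. There is still no treatment-by-occasion term, so one common treatment effect remains.

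**Check 2: code for repeated measurements**
- Each participant has one treatment, so the columns of `subjectnr*treatment` equal those of `subjectnr`.
- With one sample per visit, `subjectnr*expdelta` has one level per row and equals the residual.
- Within a participant, with J the all-ones matrix and I the identity, the covariance is therefore V = (σ²subject + σ²subject×treatment) J + (σ²subject×time + σ²residual) I. Four components enter only through two sums.
- Information rank: 2 of 4 in Part A (550 rows; eigenvalues 0, 0, 56.1, 1167.2) and 2 of 4 in Part B (220 rows; eigenvalues 0, 0, 21.9, 472.4). An ordinary inverse does not exist.
- On simulated data the REML log-likelihood is −236.1518 at each of these splits, in the order subject, subject×treatment, subject×time, residual: (0.5, 0.3, 0.2, 0.4), (0.8, 0, 0, 0.6), (0, 0.8, 0.6, 0) and (5, −4.2, −3, 3.6). All have sums 0.8 and 0.6. The last split is admissible only because NOBOUND allows negative components.

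**Check 3: does this change the inference?** Write the four-component information as A′I_rA, where A maps the four components to the two sums and I_r is the information for those sums. A has full row rank, so every generalized inverse W satisfies AWA′ = I_r⁻¹. Each Kenward-Roger quantity then equals its value in the subject-plus-residual model. Numerically, for a 6-participant arm against 8 placebo in Part A:

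| Contrast | Moore-Penrose inverse | Sweep-type inverse | Subject + residual |
|---|---|---|---|
| Average over visits | df 41.0, SE 0.4997 | df 41.0, SE 0.4997 | df 41.0, SE 0.4997 |
| Week 21 | df 105.7, SE 0.6394 | df 105.7, SE 0.6394 | df 105.7, SE 0.6394 |

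The SEs, and the Week 21 df, depend on the illustrative variances; the agreement across columns does not.

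**Check 4: another coding of occasion.** If occasion is vaccination number and `expdelta` is time since that dose, participants can have several values per `expdelta` level. `subjectnr*expdelta` then no longer duplicates the residual. The rank is 3 of 4, still singular because of `subjectnr*treatment`.

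**The case against.** The strongest case on the other side is that little follows in practice. The trial is exploratory, with no formal null hypothesis and no multiplicity adjustment (SAP 4.5.1), and the CSF objective is described as estimation (SAP 1.9). The unedited SAS output and scripts go into the statistical report (SAP 1.7) and deviations are to be documented (SAP 4.6), so a failed fit would be visible. For the single-value model, the random subject factor is in the Section 4.5 text as well as the code, so on that term the two agree. All of this stands and limits the consequence. It does not settle which CSF effect is estimated, and Section 4.5 still promises intervals and p-values from these models.

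Two stronger readings are tempting, and the documents do not support them.

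- *The singular information matrix invalidates the Kenward-Roger degrees of freedom and intervals.* Check 3 shows otherwise: the total covariance is identified, and any generalized inverse gives the same results as the subject-plus-residual model. The SAP does not say how the singularity is to be handled, so a failed or warned fit remains possible, but distorted intervals do not follow.
- *The occasion term forces the UB-312 minus placebo difference to be equal after doses 1, 2 and 3.* This needs occasion to be vaccination number and `expdelta` to be time since that dose. The SAP defines neither that way; occasion otherwise appears only as a listing column beside dosing date (SAP 4.4.1, 4.4.2). If `expdelta` is study time, the treatment-by-time term already lets the difference vary.

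**Conclusion.** The point holds as a mismatch between Appendix 2, Section 4.5 and the schedule, and should be corrected before database lock.

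The CSF and MDS-UPDRS part matters more. The single-value label conflicts with two scheduled values, and the code either merges Weeks 21 and 45 into one effect or, with one row per participant, contains an aliased variance component (rank 1 of 2). This follows from the schedule and the code.

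In the repeated code, two of four variance components are redundant. The aliasing of subject-by-treatment with subject rests only on the parallel design; that of subject-by-time with the residual also assumes one sample per visit. The ranks do not depend on the assumed variance values. The practical risks are a failed or warned fit, individual components that cannot be interpreted and may be negative, and a text/code contradiction resolved only after unblinding. Under SAP 1.5 the programs run after database lock. Degrees of freedom, standard errors and intervals are not shown to be wrong.

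**What to change.** 1. **CSF titres and MDS-UPDRS:** move them out of the single-value class in Section 4.5. Fit treatment, visit, treatment-by-visit and baseline, with subject as random factor, and report contrasts against pooled placebo separately at Week 21 and Week 45. Other CSF analytes with both visits raise the same question and should be assigned explicitly.
2. **Endpoints with truly one post-baseline value** (ELISpot appears to be one, since footnote 19 makes the EOT sample a substitute for a missed V8 sample): use ordinary ANCOVA with treatment and baseline, with no RANDOM statement and no occasion term. Amend the Section 4.5 sentence that names subject as a random factor for this model.
3. **Repeated code:** delete `subjectnr*treatment`, `subjectnr*expdelta` and occasion. What remains is random subject with treatment, time, treatment-by-time and baseline, as Section 4.5 states.

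Removing NOBOUND, or replacing the random subject effect with a REPEATED covariance structure, is optional and does not correct an error. The random-subject model does imply equal correlation between all visits over 44 weeks, so a sentence justifying that, or choosing another structure, would be useful.

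The cost is a few lines of SAS and a short edit to Section 4.5. No new data are needed.
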